### **Completing Visit 2**

Once the blood draws and all other Visit 2 procedures have been completed, study staff will issue the participant \$30.00 in compensation on a University-issued payment card, plus a parking voucher for MWH or \$5.00 for transportation reimbursement. If the \$5.00 in transportation reimbursement is issued, this is to be issued separately as an expense reimbursement

(nontaxable). Study staff will tell the participant to expect a telephone call the following business day with the results of their OGTT. Study staff will also give the participant instructions and visual materials to complete the second 24-hour dietary recall, which will occur randomly within the following 2 weeks. The participant will be told that they will be paid \$10.00 to their payment card after the second recall has been completed. Study staff will document Visit 2 in the participant’s progress notes.

**75 g or 100 g OGTT Laboratory Results**

The UPMC Clinical Laboratory will relay glucose and clinical lab results to study staff via fax within one to two business days. Clinical labs (lipid panel, high-sensitivity c-reactive peptide, and insulin) and glucose values will then be entered into the database, which will make the diagnosis of GDM based on criteria for the respective OGTT tests.

Diagnostic criteria of GDM differs between Arm A (75 g OGTT) and Arm B (100 g OGTT) as follows:

**Participants randomized to Arm A (75 g OGTT) will be diagnosed under IADPSG criteria. A positive GDM diagnosis under IADPSG criteria is  $\geq 1$  abnormal value from the 75 g test:**

Fasting glucose value	1 hour glucose value	2 hour glucose value
$\geq 92$ mg/dL	$\geq 180$ mg/dL	$\geq 153$ mg/dL

**Participants randomized to Arm B (100 g OGTT) will be diagnosed under Carpenter-Coustan criteria. A positive GDM diagnosis under Carpenter-Coustan criteria is 50 g GCT  $\geq 130$  mg/dL (value from Visit 1) and  $\geq 2$  abnormal values from the 100 g test:**

Fasting glucose value	1 hour glucose value	2 hour glucose value	3 hour glucose value
$\geq 95$ mg/dL	$\geq 180$ mg/dL	$\geq 155$ mg/dL	$\geq 140$ mg/dL

### *“Mild GDM”*

For the purposes of study outcomes, the study database will automatically designate participants completing the 100 g OGTT (Arm B) that meet one of the three criteria listed below as “Mild GDM”.

1. 50 g GCT  $\geq$ 130 mg/dL **and** 0 or 1 abnormal values from 100 g OGTT (by Carpenter-Coustan criteria)
2. 50 g GCT  $<$ 130 mg/dL **and** 1, 2, 3, or 4 abnormal values from 100 g OGTT (by Carpenter-Coustan criteria)
3. 100 g OGTT fasting value  $\geq$ 92 mg/dL

This is **not** a clinical diagnosis, and participants meeting these criteria will be reported to providers as having a negative GDM diagnosis as they would not have been diagnosed under current clinical criteria. For the purposes of this study, all participants designated as having “Mild GDM” will be selected to return for Visit 3 at 12-months postpartum.

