## **Blinding**

Providers are blinded to which test their patient completed and the patient's numerical test results. Study staff will notify providers as to whether or not their patient has GDM; they will not be told the specific glucose values. Providers will administer care based on the reported diagnoses. Study investigators, including the PI, will remain blinded to the randomization schema and study outcomes until the completion of the study. The PI or co-investigators will only be unblinded in the following cases:

- 50 g glucose value of  $\geq 200$  mg/dL
- 100 g OGTT fasting value  $> 105$  mg/dL or 2 hour value  $> 200$  mg/dL, if 50 g GCT  $> 130$  mg/dL
- Any severe adverse event that warrants further medical intervention
- Symptomatic reactive hypoglycemia ( $< 55$  mg/dL)

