### *Unblinding Providers to OGTT Results*

If a participant’s 50 g GCT value is  $\geq$ 130 mg/dL, and their 100 g OGTT fasting value is  $\geq$ 105 mg/dL or 2 hour value is  $\geq$ 200 mg/dL, their provider will be unblinded to their results for ethical and safety reasons, so treatment for GDM can be initiated. These participants would not normally be diagnosed in clinical practice because they had a normal 50 g GCT. These safety thresholds were used in the HAPO Study (Metzger, BE, et al., *N Engl J Med* 2008). Study staff will alert the participant’s provider of their results through Epic (or fax for Epic non-users). The study physician will also notify participants via telephone.

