### *OGTT Result Reporting*

Participants will be notified of their 75 g or 100 g OGTT results within 1 or 2 business days of testing. Study staff will notify participants of a negative diagnosis by telephone or letter. In cases of positive GDM diagnosis, study staff will notify the study physician, who will directly call the participant with her diagnosis, answer any questions, and relay that she is to follow up with her provider for treatment. The participant's providers will be notified via Epic letter and encounter or a fax, informing them of the positive or negative GDM diagnosis. Study staff will also document results and notifications in the participant's progress notes. Epic encounters and letters are from [name], Department of Maternal-Fetal Medicine, routed to the participant's OB provider. (See [Appendix G](#).)

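### The third Mild GDM criterion also captures Arm B women who do have GDM, so the manual has the same women reported both positive and negative

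*Protocol*

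**What the plan says.** Three sections of the protocol (the Manual of Procedures) decide what an Arm B woman and her provider are told after Visit 2.

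- **75 g or 100 g OGTT Laboratory Results.** The study database receives the values, "which will make the diagnosis of GDM based on criteria for the respective OGTT tests". For Arm B, "A positive GDM diagnosis under Carpenter-Coustan criteria is 50 g GCT" of at least 130 mg/dL together with at least two abnormal values on the 100 g test. Abnormal means fasting ≥95, 1-hour ≥180, 2-hour ≥155 or 3-hour ≥140 mg/dL.
- **Mild GDM.** The database automatically gives this label to any Arm B woman who meets one of three criteria: (1) GCT ≥130 with no or one abnormal value; (2) GCT <130 with one to four abnormal values; (3) "100 g OGTT fasting value $\geq$ 92 mg/dL". The section then says that "participants meeting these criteria will be reported to providers as having a negative GDM diagnosis as they would not have been diagnosed", by the standard of present clinical practice.
- **OGTT Result Reporting.** "In cases of positive GDM diagnosis, study staff will notify the study physician, who will directly call the participant with her diagnosis", and the provider is informed as well.

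Two further sections bear on the consequence. Blinding keeps the numerical results from providers and adds: "Providers will administer care based on the reported diagnoses". Unblinding Providers to OGTT Results sets a safety exception: with GCT ≥130 and either fasting ≥105 or 2-hour ≥200, "their provider will be unblinded to their results for ethical and safety reasons, so treatment for GDM can be initiated".

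**The concern.** Criteria 1 and 2 each carry a limit that keeps them apart from the Arm B definition of GDM. Criterion 3 has no GCT condition, no cap on the number of abnormal values and no exclusion of women already diagnosed. A woman can therefore satisfy the GDM definition and criterion 3 together. The reporting section then requires a positive report and the Mild GDM section a negative one. The reason given for the negative report, that she would have gone undiagnosed, is untrue for her. No sentence says which rule prevails.

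Because providers act on the reported diagnosis without seeing the values, a woman reported negative by mistake could go untreated. There are few routes to correction during pregnancy: the principal investigator is also blinded and has limited database access (Manual Data Entry), and the numerical results enter the medical record only after all participants have delivered (Visit 2 Results Back Entry).

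Separately, the label is assigned for study outcomes, so one woman can carry both the GDM and the Mild GDM label.

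**Working it through.** The protocol states no figure for this overlap, so there is none to reproduce. The check is logical.

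**Step 1: does criterion 3 overlap with GDM?** A fasting value ≥95 is also ≥92, so every GDM-positive woman with an abnormal fasting value meets criterion 3. So does a GDM-positive woman with fasting 92–94 and two abnormal post-load values. Two examples (mg/dL):

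- GCT 140, fasting 97, 1-hour 190, 2-hour 150, 3-hour 120. Fasting and 1-hour are abnormal, so she has GDM; 97 ≥ 92, so she also meets criterion 3.
- GCT 150, fasting 93, 1-hour 185, 2-hour 160, 3-hour 130. The 1-hour and 2-hour values are abnormal, so she has GDM; 93 ≥ 92, so she also meets criterion 3.

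Neither reaches fasting 105 or 2-hour 200, so the provider-unblinding rule does not reach them.

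**Step 2: which patterns are affected?** Band each value at the cut-offs the protocol uses: fasting <92, 92–94, 95–104, ≥105; 1-hour below 180 or not; 2-hour <155, 155–199, ≥200; 3-hour below 140 or not. At GCT ≥130 this gives 4 × 2 × 3 × 2 = 48 patterns.

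For each fasting band there are 2 × 3 × 2 = 12 post-load patterns: 1 with no abnormal value, 4 with one, 5 with two and 2 with three.

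- Fasting normal (<95): GDM needs at least two abnormal post-load values, 5 + 2 = 7 patterns per band.
- Fasting abnormal (≥95): GDM needs at least one, 4 + 5 + 2 = 11 patterns per band.

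| Fasting (mg/dL) | GDM-positive | Also meets criterion 3 | Of these, provider unblinded as written | Left |
|---|---|---|---|---|
| <92 | 7 | 0 | 0 | 0 |
| 92–94 | 7 | 7 | 3 | 4 |
| 95–104 | 11 | 11 | 4 | 7 |
| ≥105 | 11 | 11 | 11 | 0 |
| Total | 36 | 29 | 18 | 11 |

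Criteria 1 and 2 overlap with none of the 36.

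**Step 3: how far does the safety exception help?** As written it covers 18 of the 29, leaving 29 − 18 = 11, all with fasting 92–104 and 2-hour <200. But that section explains the exception by saying these women would normally go undiagnosed "because they had a normal 50 g GCT", which does not fit its condition of GCT ≥130. If <130 was meant, it covers none of the 29. The range is therefore 11 to 29.

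**Step 4: what would an exclusion remove?** With both GCT bands there are 96 patterns. As written, 29 are both GDM and Mild GDM, 7 GDM only, 59 Mild GDM only and 1 neither. With GDM-positive women excluded from criterion 3, 36 are GDM only, 59 Mild GDM only, 1 neither and none both.

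Among women without GDM, the only pattern criterion 3 adds to criteria 1 and 2 is GCT <130, fasting 92–94 and normal post-load values. That is evidently its target, and the exclusion keeps it.

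**The case against.** The strongest defence is that the intended order can be read from context. The laboratory-results section holds the only diagnostic rule for Arm B. The Mild GDM section describes its label as a research designation and not a clinical diagnosis, and it ties the negative report to women who would have gone undiagnosed. OGTT Result Reporting makes no exception for positive results. Postpartum Telephone Encounters lists GDM, Mild GDM and women without GDM as separate groups. On this view a phrase is missing and no reader would be misled.

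It can also be said that pattern counts carry little information, that no outcome under Data Collection Associated with Study Outcomes depends on the label, that grouping of dual-labelled women in the analysis may be settled in an SAP, and that a check of past reports presumes an error nobody has shown.

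Much of this stands. An exclusion was probably intended, the counts say nothing about frequency, and no misreporting is shown. Selection for postpartum follow-up is unaffected, because GDM and Mild GDM are both followed.

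It does not remove the contradiction. The remark about women going undiagnosed is a reason, not a condition, and it is false for the overlap group. Criteria 1 and 2 spell out their limits while criterion 3 has none. A database that assigns the label automatically applies conditions and does not infer intent. The check of past reports is proportionate because the manual does not show how the database was programmed.

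**Conclusion.** The concern holds: the rule is wrong as written. Any Arm B woman with GDM under the protocol's own definition and a fasting value of at least 92 mg/dL also meets the third Mild GDM criterion, and the text then calls for both a positive and a negative report.

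The overlap takes in 29 of the 36 GDM-positive patterns. In 11 of them no safety exception applies as written, and in all 29 if the unblinding rule was meant for GCT <130. How many women this represents cannot be derived, because the protocol gives no frequencies.

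Clinical harm would arise only if the Mild GDM text were put ahead of the diagnostic and reporting sections. The conclusion that the text contradicts itself does not depend on that. It should be fixed, because providers treat on the label alone and the correction is nearly free.

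**What to change.** In the Mild GDM section, state that the three criteria apply only to Arm B participants who do not meet the Arm B definition of GDM in the laboratory-results section. Add that a diagnosis under that definition is always reported as positive under OGTT Result Reporting, whatever the fasting value.

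Then confirm that the database logic follows this order, and check the reports already sent for Arm B women with a GDM diagnosis and fasting ≥92 mg/dL.

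The cost is two short sentences in the manual, one check of the database logic and one check of the reports for an identifiable subset.

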### *Critical Glucose Values*

If a participant’s blood glucose values are critical, indicating hypoglycemia ( $<$ 55 mg/dL) or hyperglycemia ( $>$ 250 mg/dL), the UPMC CLB will follow clinical procedure for clinical values by performing a repeat or verification test. If glucose values remain critical after the confirmatory test, study staff will be contacted by the UPMC CLB with the results and follow up with the participant. If participant is non-symptomatic and the database determines the glucose value to be a Severe Adverse Event, [name] is to be notified. For participants who exhibit symptoms of hypo/hyperglycemia, the Maternal-Fetal Medicine fellow on call is to be contacted at [contact] for consultation. [name] will also be notified. These events will be documented in the participant’s progress notes.

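### The safety rule for unblinding providers is printed for a positive 50 g GCT but justified by a normal one, so as printed it misses every over-limit Arm B woman with a GCT below 130 mg/dL

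*Protocol*

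**What the plan says.** Five parts of the Protocol (Manual of Procedures, Version V) bear on this.

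- **75 g or 100 g OGTT Laboratory Results.** An Arm B diagnosis needs a GCT of at least 130 mg/dL and at least two abnormal values on the 100 g test (fasting ≥95, 1 h ≥180, 2 h ≥155, 3 h ≥140).
- **Mild GDM.** Criterion 2 covers a GCT below 130 with one to four abnormal values. The label is not a clinical diagnosis, and "participants meeting these criteria will be reported to providers as having a negative GDM diagnosis". No exception is stated.
- **Unblinding Providers to OGTT Results.** If the GCT is ≥130 and the 100 g fasting value is ≥105 or the 2-hour value is ≥200, "their provider will be unblinded to their results for ethical and safety reasons, so treatment for GDM can be initiated". The next sentence gives the reason: "These participants would not normally be diagnosed in clinical practice because they had a normal 50 g GCT".
- **Blinding.** Providers get the diagnosis without the numbers, and "Providers will administer care based on the reported diagnoses". The list of cases in which the PI or co-investigators are unblinded includes a fasting value above 105 or a 2-hour value above 200 "mg/dL, if 50 g GCT $> 130$ mg/dL".
- **OGTT Result Reporting.** Providers receive a message "informing them of the positive or negative GDM diagnosis".

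**The concern.** A GCT of 130 or more is the positive screen in this trial, so it cannot also be the normal GCT that the reason describes. Either the condition or the reason is wrong. The Blinding section prints the same direction, so a single misread symbol is an unlikely explanation.

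A safety rule is at stake. Women with a GCT below 130 do take the 100 g test, because Randomization Procedures randomises everyone below 200. If one of them exceeds the study's own safety limits, the manual as printed has her reported as negative, and her care follows that report. She belongs to the group that the rule's own reason describes. The printed condition also mainly releases numbers for women already reported as GDM-positive, who need no unblinding to be treated.

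**Working it through.** The plan gives no figure to reproduce. The check applies the printed rules in order.

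**1. Every over-limit woman with a GCT below 130 is Mild GDM.** A fasting value ≥105 is also ≥95, and a 2-hour value ≥200 is also ≥155. Each such woman therefore has at least one abnormal value and meets Mild GDM criterion 2. She cannot be GDM, because that needs a GCT ≥130. She does not meet the unblinding rule, for the same reason.

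Example: GCT 125, fasting 110, 2 h 205. She has at least two abnormal values, is not GDM, is Mild GDM, is reported negative, and her provider is not unblinded.

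**2. No other stated results rule sends her values to the provider in pregnancy.**
- Critical Glucose Values (Visit 2) starts, on the high side, only above 250 mg/dL, and then "study staff will be contacted by the UPMC CLB with the results and follow up with the participant". The on-call Maternal-Fetal Medicine fellow is brought in for symptomatic women.
- OGTT Result Reporting sends only positive or negative.
- Visit 2 Results Back Entry releases numbers only once all participants have delivered.
- The Blinding list adds severe adverse events that need intervention and symptomatic hypoglycaemia, and it concerns the investigators.

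**3. Count of rule patterns.** Cut each input where a rule cuts it: GCT 2 levels (<130, ≥130), fasting 4 (<92, 92–94, 95–104, ≥105), 1 h 2 (<180, ≥180), 2 h 3 (<155, 155–199, ≥200), 3 h 2 (<140, ≥140).

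- All patterns: 2 × 4 × 2 × 3 × 2 = 96, or 48 at each GCT level.
- Over the limit at each GCT level: fasting ≥105 gives 1 × 2 × 3 × 2 = 12. Fasting <105 with 2 h ≥200 gives 3 × 2 × 1 × 2 = 12. Total 24.
- GCT ≥130 and undiagnosed (one abnormal value only): fasting ≥105 alone, 1 pattern; 2 h ≥200 alone with fasting <92 or 92–94, 2 patterns. Total 3, so 24 − 3 = 21 are GDM.

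| Over-limit patterns | GCT <130 | GCT ≥130 |
|---|---|---|
| Total | 24 | 24 |
| Diagnosed GDM | 0 | 21 |
| Not diagnosed | 24 | 3 |
| Provider unblinded as printed | 0 | 24 |

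Undiagnosed and over the limit: 24 + 3 = 27. Coverage of these 27:
- as printed: 3/27 = 11%;
- with the condition reversed to <130: 24/27;
- with the limit applied to any undiagnosed Arm B woman: 27/27, releasing none of the 21.

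**4. Check in 1 mg/dL steps.** Fasting 60–259 (200 values) and 2 h 100–259 (160 values) give 32,000 pairs. Of these, 45 × 100 = 4,500 are below both limits, which leaves 27,500. With two GCT values (100, 129), two 1-hour values (179, 180) and two 3-hour values (139, 140), that is 27,500 × 8 = 220,000 over-limit combinations with a GCT below 130. None meets the printed rule, and all are Mild GDM.

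**5. Independent grid of boundary values.** With a GCT below 130, 0 of 1,536 over-limit profiles are unblinded and all 1,536 are Mild GDM. With a GCT ≥130, all 3,072 trigger the rule and 2,720 are already GDM; the other 352 have one abnormal value.

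**6. Boundaries.** The provider rule uses ≥ and the investigator list uses >. With a GCT of 140, a woman whose only over-limit value is a fasting value of exactly 105, or a 2-hour value of exactly 200, meets the first but not the second.

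**The case against.** The strongest reply is that this is a reversed sign which anyone who reads the reason would correct. The reason makes the likely intent clear, no misreporting is shown, and the Mild GDM section only does what a two-arm comparison of criteria requires. Much of that is fair: the error lies in the unblinding rule, and the line about negative reporting is where its consequence appears. But the Blinding section repeats the direction, the database assigns Mild GDM automatically, and nothing shown says which GCT condition is applied to unblinding. If the condition is right and the reason is the misprint, the normal-GCT women are left out with no reason given.

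The percentages depend on how values are binned, and this point stands. Without the fasting cut at 92, there are 20 + 2 = 22 undiagnosed over-limit patterns and coverage is 2/22 = 9%. The independent grid gives 352/(1,536 + 352) = 19%. The result of zero for a GCT below 130 follows from the rules and does not depend on binning.

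It can also be said that reversing the sign is enough, and that covering every undiagnosed woman goes beyond the stated reason. Reversal alone, however, would withdraw cover from women with a GCT ≥130 and one very high value, whom the printed rule now protects. The mismatch of > and ≥ is minor and matters only at exact boundary values.

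**Conclusion.** The rule is wrong as written. Its condition contradicts its reason, and as printed it covers none of the over-limit Arm B women with a GCT below 130, all of whom are reported negative. In patterns it reaches 3 of 27 undiagnosed cases, and 21 of its 24 triggers are already GDM-positive.

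These are counts of rule combinations. The document gives no rates from which to derive a number of women. The conclusion assumes only that the printed rules are followed. Staff or the database may in fact apply a GCT below 130, and Appendix G, with its reporting templates, is not shown. No actual misreporting is claimed, nor any effect on the randomised comparison. Confidence in the contradiction is high. It should be corrected because it concerns safety and the correction is cheap.

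**What to change.** Reword Unblinding Providers to OGTT Results so that it applies to any Arm B participant not diagnosed with GDM, whatever her GCT, whose 100 g fasting value is ≥105 mg/dL or 2-hour value is ≥200 mg/dL. Give the reason as a normal GCT or only one abnormal value. This is sound whichever sentence was misprinted.

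Use the same condition and the same ≥ signs in Blinding. Add a cross-reference to the exception in the Mild GDM section and in OGTT Result Reporting.

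Confirm which GCT condition the database or staff have applied. List from stored values every Arm B woman with a GCT below 130 who was over either limit, and check that her provider was told.

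The cost is wording in four sections and one query, with no new tests. If the printed rule was in use, some more Arm B women would be treated, which slightly narrows the contrast between arms. The Protocol already accepts that price on ethical and safety grounds.

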### *Unblinding Providers to OGTT Results*

If a participant’s 50 g GCT value is  $\geq$ 130 mg/dL, and their 100 g OGTT fasting value is  $\geq$ 105 mg/dL or 2 hour value is  $\geq$ 200 mg/dL, their provider will be unblinded to their results for ethical and safety reasons, so treatment for GDM can be initiated. These participants would not normally be diagnosed in clinical practice because they had a normal 50 g GCT. These safety thresholds were used in the HAPO Study (Metzger, BE, et al., *N Engl J Med* 2008). Study staff will alert the participant’s provider of their results through Epic (or fax for Epic non-users). The study physician will also notify participants via telephone.

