### **Visit 2 Results Back Entry**

Once all participants have completed their Visit 2 and delivered, study staff will back-enter all Visit 2 glucose results into participants' Epic EMR for clinical use post-study. At this time, providers will be unblinded to the specific numeric results of their patients' testing, and whether they completed the 75 g or 100 g OGTT. Participants may also request that a paper copy of their results be sent to them after they deliver.

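### The Arm B safety unblinding rule requires a 50 g GCT of at least 130 mg/dL although its stated reason is a normal GCT, so as written it reaches no woman with GCT below 130

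*Protocol*

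**What the plan says.** - **Diagnosis in Arm B** (Protocol, 75 g or 100 g OGTT Laboratory Results): "A positive GDM diagnosis under Carpenter-Coustan criteria is 50 g GCT" at or above 130 mg/dL together with at least two abnormal values on the 100 g test. The cut-offs are 95 fasting, 180 at 1 hour, 155 at 2 hours and 140 at 3 hours (mg/dL).
- **Mild GDM**: criterion 1 covers GCT of 130 or more with no or one abnormal value. Criterion 2 covers GCT below 130 with one to four abnormal values. These women are "reported to providers as having a negative GDM diagnosis as they would not have been diagnosed under current clinical criteria". No exception is stated.
- **Unblinding Providers to OGTT Results**: if GCT is 130 or more and the 100 g fasting value is at least 105 or the 2-hour value at least 200, "their provider will be unblinded to their results for ethical and safety reasons, so treatment for GDM can be initiated". The next sentence gives the reason: "These participants would not normally be diagnosed in clinical practice because they had a normal 50 g GCT".
- **Blinding**: "The PI or co-investigators will only be unblinded in the following cases". The list includes the same fasting and 2-hour limits, again tied to a GCT above 130, but with strict inequalities throughout. It also includes a severe adverse event that needs medical intervention.
- **Critical Glucose Values** (Visit 2): for a confirmed value above 250 mg/dL, "study staff will be contacted by the UPMC CLB with the results and follow up with the participant", whatever the GCT.
- **OGTT Result Reporting**: "Study staff will notify participants of a negative diagnosis by telephone or letter". The provider is told the same.
- **Visit 2 Results Back Entry**: numeric results enter the medical record "Once all participants have completed their Visit 2 and delivered". A participant may ask for a paper copy after she herself delivers.

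**The concern.** The trigger and the reason for the safety rule contradict each other. A GCT of 130 or more is what the protocol elsewhere treats as a positive screen, so a woman who meets the trigger did not have a normal GCT. A woman who fits the reason, with a normal GCT and very high OGTT values, does not meet the trigger.

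This matters because the protocol itself sets the limits on ethical and safety grounds and names treatment as the purpose. All women with a GCT below 200 are randomized, so Arm B includes women with GCT below 130, and the study holds their full OGTT results. Routine care would not have tested them further. The defect is that the study has the result, has fixed a level for acting on it, and the written rule misses the women it was said to be for.

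**Working it through.** No figure in the protocol needs reproducing. The check applies the written rules in order. All glucose values are in mg/dL.

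**1. Two worked profiles**

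| | Profile 1 | Profile 2 |
|---|---|---|
| GCT | 120 | 135 |
| OGTT fasting / 1 h / 2 h / 3 h | 110 / 190 / 205 / 145 | 106 / rest normal |
| Abnormal values | 4 (110≥95, 190≥180, 205≥155, 145≥140) | 1 (106≥95) |
| GDM diagnosis | No, GCT below 130 | No, only one abnormal value |
| Mild GDM | Yes, criterion 2: reported negative | Yes, criterion 1: reported negative |
| At or above a safety limit | Both (110≥105, 205≥200) | Fasting (106≥105) |
| Provider unblinded | No, GCT below 130 | Yes |
| Critical value above 250 | No | No |

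The rule acts on the milder profile and not on the more severe one. Profile 2 also shows a smaller conflict: the provider is unblinded for treatment while the Mild GDM section has her reported negative.

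**2. A grid of profiles** (combinations of values, not patients)

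GCT 100, 129, 130, 131, 199; fasting 85, 92, 95, 104, 105, 106, 120; 1 h 150, 180; 2 h 120, 155, 199, 200, 201, 240; 3 h 120, 140.

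- Fasting and 2-hour pairs at or above a limit: 7×6 − 4×3 = 30. With two 1-hour and two 3-hour values, 30×4 = 120 for each GCT value.
- GCT below 130: 2×120 = 240 profiles. None is diagnosed, all are Mild GDM, and 0 of 240 are caught by the provider rule or by the Blinding list.
- GCT of 130 or more: 3×120 = 360 profiles, all caught by the provider rule. An isolated high fasting value gives 3 profiles per GCT value and an isolated high 2-hour value gives 3×2 = 6, so 3×(3+6) = 27 have one abnormal value. The other 360 − 27 = 333 have at least two and are already diagnosed. This takes the diagnosis to prevail over Mild GDM criterion 3 (fasting 92 or more), an order the protocol does not state.

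**3. Boundary values**

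The provider rule uses at least 130, 105 and 200; the Blinding list uses above 130, 105 and 200. Values exactly at these limits can satisfy the first and not the second.

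**4. Arm A**

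No such rule is needed there. A fasting value of 105 or a 2-hour value of 200 is already positive on the 75 g test (limits 92 and 153).

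**5. Effect of possible changes**

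- Reversing the sign to GCT below 130 would catch the 240 and lose the 27.
- Deleting the GCT condition catches 240 + 360 = 600 of 600. The limits exceed the diagnostic cut-offs (105≥95, 200≥155), so each such woman has at least one abnormal value. She is then either diagnosed already or dependent on this rule.

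**The case against.** The strongest reply is that this is a drafting slip. The reason stands beside the trigger, so staff may have applied the rule as intended. The database makes the diagnosis, and the notification templates sit in an appendix that is not shown. That may be so, and it limits what can be concluded. It does not repair the text: Blinding repeats the same direction and nothing else in the protocol corrects it. A misread sign is unlikely for the same reason, and because the Mild GDM section prints both directions.

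A second reply is that these women are not left without follow-up. This stands. A reader might infer that nothing at all happens to a woman with GCT below 130 and high OGTT values. In fact any abnormal value makes her Mild GDM, with postpartum calls and Visit 3 testing; an abnormal laboratory finding can be an adverse event; and values above 250 or a severe adverse event have their own routes. What is missing is a stated trigger for treatment in that pregnancy when fasting is 105 to 250 or the 2-hour value 200 to 250 and no severe adverse event occurs.

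A reader might also infer that numeric results are withheld until the whole cohort has delivered. That holds for entry in the record, but a participant can obtain a paper copy after her own delivery. Either comes too late for treatment in that pregnancy.

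**Conclusion.** The contradiction is certain on the text and rests on no assumption about rates. As written, the safety rule excludes every Arm B woman with GCT below 130. For GCT of 130 or more it is not empty, but its only added treatment trigger is for women with a single abnormal value at or above a limit, whom the stated reason does not describe.

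A reader might infer that women were in fact left untreated, or attach a number to them. The document supports neither. It does not show whether the database follows the text or the reason. It gives neither the share of Arm B with GCT below 130 nor the share of those at or above a limit, so no count can be derived; the grid counts show logic, not frequency. Nor does the point show any error in an endpoint, analysis or sample size. It is a safety rule that gives a wrong result as written and should be corrected.

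**What to change.** 1. **Unblinding Providers to OGTT Results**: delete the GCT condition, so that the provider is unblinded for any 100 g OGTT participant with fasting at least 105 or 2-hour at least 200 mg/dL. Replace the reason with: *some of these participants would not be diagnosed because of a normal 50 g GCT or only one abnormal value.* Do not simply reverse the sign, which would drop the isolated-value women. Deletion also keeps the early numeric results that providers of women already diagnosed receive under the present rule.
2. **Blinding**: make the same change in the list for the PI and co-investigators, using at least rather than above.
3. **Mild GDM**: except participants under the safety rule from negative reporting.
4. **Database**: have the data center check that the database rule and the notification template match the corrected text. Query Arm B women already tested with GCT below 130 and a value at or above a limit, and establish how each was handled.
5. **Analysis**: keep each woman's Carpenter-Coustan diagnosis unchanged and report the safety-rule women separately.

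The cost is wording in three sections, one check and one query, with no new test or visit. The downside is that a few more Arm B women may be treated than under Carpenter-Coustan alone, and their providers are unblinded; separate reporting makes this visible.
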